2.3 Secondary Outcomes

- 2.3a CD4+ T cell numbers that recently emigrated from the thymus
- 2.3b Blood CD4+ T cell count
- 2.3c Complete blood cell count, comprehensive metabolic panel
- 2.3d Incidence of opportunistic infection
- 2.3e Antibody response to annual influenza vaccination

3.0 STUDY DESIGN

This is an open-label, randomized Phase II trial to determine whether MMF given over 22 months meaningfully decreases the size of the HIV reservoir.

At the University of Washington in Seattle, we will enroll 5 study participants who have been on ≥ 2 years of suppressive ART. Study participants will be followed closely for at least 22 months with safety labs and serial measurements of the HIV reservoir (specifically, cell-associated HIV DNA and mRNA (**ca-DNA & ca-RNA**), quantitative viral outgrowth assay (**QVOA**), and single copy plasma viral

Clinical Protocol

load (**scVL**)). A “go/no-go” decision will occur after 12 months based on pre-defined thresholds of reduction in the HIV reservoir measured with ca-DNA.

All participants will be offered enrollment in a sub-study in which an anoscopy with rectum biopsies is performed on 3 occasions to assess the reservoir in the gastrointestinal lymphatic tissue (**GALT**).

We will vaccinate study participants with the annual influenza vaccine and analyze their humoral response to this vaccine approximately one month later with a routine blood draw done in conjunction with a safety labs blood draw.

We hypothesize that low doses of MMF will be well tolerated among healthy HIV-infected study participants who have fully ART-suppressed HIV. We hypothesize that the incidence of opportunistic infections will not exceed that of comparable larger cohorts of HIV-treated patients. Of note, certain opportunistic infections such as herpes zoster or HSV-2 recurrence continue to occur despite suppressive ART, while pneumocystis pneumonia, CMV end organ disease, cryptococcus and many other opportunistic infections are much less common in this context. Therefore, in the event of an infection, we will confer with the data safety management (DSM) panel to discuss whether this event is directly attributable to MMF. Finally, we hypothesize that peripheral blood CD4+ and CD8+ T cell counts will remain unchanged throughout MMF therapy, and that HIV replication will remain controlled on ART with addition of MMF.

We hypothesize at least a 0.25-log reduction in cell-associated HIV DNA at one-year intervals in study participants who have a demonstrated anti-proliferative response to MMF treatment. We hypothesize that cell-associated HIV DNA will undergo a shift from predominant residence in T_{CM} and T_{EM} to predominant residence in T_N and T_{SCM} . In regards to our sub-study, we predict that reservoir depletion will occur with equivalent rates in blood and GALT.

4.0 SELECTION AND ENROLLMENT OF SUBJECTS

4.1 Inclusion Criteria

- a. Confirmed HIV infection, by two different positive antibody tests and/or detectable plasma HIV RNA on two different dates
- b. ≥ 18 and ≤ 65 years of age
- c. Continuous ART during the last two years, with current ART preferably including an integrase inhibitor
- d. HIV RNA <40 copies / mL on four occasions during continuous ART of ≥ 2 years with no more than one blip of <1000 HIV RNA copies / mL
- e. CD4+ T cell count $> 350/\text{mm}^3$ within the past 365 days
- f. Karnofsky score ≥ 80
- g. Plan to reside in area 2 years
- h. Consents to study
- i. “Step 1” lead-in phase: Tolerability of MMF during one week dose escalation of 500 mg once daily (or Myfortic \odot 360 mg once daily)

Clinical Protocol

- j. "Step 2a" lead-in phase: Demonstrated tolerability and anti-proliferative effect (>= 80% anti-proliferative effect) of one week of MMF 500 mg twice daily (or Myfortic[®] 360 mg twice daily)
- k. "Step 2b" lead-in phase (only if necessary based on inadequate anti-proliferative effect on 500 mg bid): Demonstrated tolerability and anti-proliferative effect (>= 80% anti-proliferative effect) of one week of MMF 750 mg twice daily (or Myfortic[®] 540 mg twice daily)

4.2 Exclusion Criteria

- a. Active malignancy including skin cancer, myelodysplastic syndrome, or myeloproliferative disease within 24 weeks prior to study entry
- b. Prior organ or bone marrow transplantation
- c. Diagnosed autoimmune disease
- d. Medical need for ongoing treatment with an immunosuppressive drug
- e. Diagnosis of AIDS (defined as any AIDS-defining opportunistic infection or cancer, or a history of blood CD4+ T cell count < 200/ μ L)
- f. Active opportunistic infection
- g. Using disallowed medications (see 4.3)
- h. Vomiting or diarrhea which prohibits consistent use of study drugs
- i. Pregnant, intention to become pregnant, or breastfeeding
- j. Woman of child bearing age who are NOT using two forms of birth control OR practicing complete abstinence
- k. Excessive ingestion of ethanol, determined by an AUDIT score of >8
- l. Substance abuse
- m. History of medical non-compliance
- n. Quantiferon TB positive
- o. The following laboratory values (<30 days before enrollment):
 - Hemoglobin < 8.5 mg/dL
 - Absolute neutrophil count < 1000 cells/mm³
 - ALT > 2 x upper limit of normal
 - Platelet count \leq 100,000/uL
 - Creatinine clearance < 60 mL/min

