Limited Interview/Limited PE		X	X	X		
Limited Interview only (no PE)						
Discussion of MMF side effects	X	X				
Obtaining consent	X					
MMF Drug 500mg MMF for the first week, then go up to 2x500mg for the second week			Dispense x1 week	Dispense x2 weeks		Dispense x2 wks or x5 wks
Urine PG---all visits with safety labs	0	0	0	0		0
PT/PTT (Pre-BIOP safety) blue	4.5					
CBC & Diff Lavender Hemogard Tube)	3	3	3	3		3
Comp Panel (3.5mL SST)	3.5	3.5	3.5	3.5		3.5
CD4/CD8 (Lavender Top Tube)	4	4	4	4		4
MMF Levels (at HMC) (3.5mL SST)		3.5		3.5	3.5	
HCABX & HBSAGX (only-as needed) (5mL SST)	5					
TB IGRA (only-as needed) (3 Quantiferon-TB Gold Tubes 1 mL each	3					
Low Level VL Assay (10mL EDTA)		0				20
QVOA		100				
Anti-Proliferation Assay (3.5mL SST)		7		3.5	3.5	
8.5mL Yellow ACD tubes for Anti Proliferation Assays, FACS for Ki67, TREC level PCR, Cell-associated DNA and mRNA ddPCR, PBMC and plasma banking			85	8.5	8.5	
2.5 mL PAXgene Blood RNA Tube for [name] Lab		5		5		2.5
MLs	23	211	10.5	31	15.5	142
Rolling volumes/8 weeks (max 450mL)		234.0	244.5	275.5	291.0	291
TEAspoons	4.7	42.8	2.1	6.3	3.1	433.0
TABLEspoons	1.6	14.3	0.7	2.1	1.0	448.5
						0.0
						28.8
						3.1
						0.0
						9.6
						1.0
Eligibility	Entry	week 1	week 2 T	week 2 P	week 3	week 4 T
						week 4 P

Phone call to stop MMF in case of lacking efficacy by anti-proliferation test

Clinical Protocol

BIOP						
week 60	wk 74 T	wk 74 P	wk 88 T	wk 88 P	week 90	
Mo. 15	Mo. 18.5	Mo. 18.5	Mo. 22	Mo. 22	Mo. 22.5	ConVF
						PreDC
X	X		X			X
R	R					
0	0		0		0	0
3	3		3		3	3
3.5	3.5		3.5		3.5	3.5
4	4		4		4	4
3.5	3.5	3.5	3.5	3.5	3.5	
20	20		0		20	20
			100			
3.5	3.5	3.5	3.5	3.5		
212.5	212.5	8.5	119	8.5		
5	5		5			
255	255	15.5	241.5	15.5	14	20
255.0	255.0	270.5	241.5	257.0	271.0	
51.7	51.7	3.1	49.0	3.1	2.8	4.1
17.2	17.2	1.0	16.3	1.0	0.9	1.4
week 60	week 74	week 74	week 88	week 88	week 90	

The bottom row in red indicates rolling blood volumes over 8 weeks prior to and including each blood draw and should not be higher than a total of 450 mL as per University of Washington policy.

Clinical Protocol

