6.0 PARTICIPANT MANAGEMENT

6.1 Procedures

Participants in this study will take 500 mg MMF once per day for one week as a lead in to limit drug-related side effects. Provided they are tolerating the drug at lower dose, they will then initiate 500 mg MMF twice a day for 22 months in addition to their regular anti-HIV treatment. MMF will be switched to Myfortic© in the event of poorly tolerated nausea, vomiting or diarrhea and participant agreement to remain in the study. As described above, dose escalation to 750 mg MMF twice daily is possible in the event of an inadequate anti-proliferative effect. Participants will visit the clinic and provide samples (blood and optional rectal biopsies) several times during the course of the study. If feeling nausea or vomiting, participants will be offered ondansetron 4mg oral tablets. The specific procedures for the study visits are outlined below.

Eligibility Visit (approximately 2 hours)

Clinical Protocol

During this visit, we will do the following:

- 1) Provide participants with general information about the 2 West Clinic
- 2) Ask participants to sign the Study Consent Form, the Release of Medical Information Form, and HIPAA Authorization Form
- 3) Document that participants have HIV by medical records and also determine if participants have a medical condition that would preclude them from entering the study. In the event that documentation is unavailable, we will ask participants to allow us to do these tests after counseling and obtaining their verbal consent
- 4) Take a medical and medication history
- 5) Assess substance use history, including alcohol, and sexual risk behavior
- 6) Perform a general clinical exam (including vital signs: weight, height, blood pressure, pulse and temperature)
- 7) Obtain a urine specimen for pregnancy testing in female participants
- 8) Draw about 5 teaspoons of blood for routine blood tests (blood cell counts and signs of anemia, kidney or liver dysfunction)
- 9) Perform blood testing for hepatitis B and C if results are not already available from within 12 months prior to eligibility visit.

Entry Visit (approximately 1 hour) / Step 1 Lead-in

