6.2 Toxicity

The participants will undergo standardized clinical evaluations at each visit. The evaluations will include an interim medical history, symptom-directed exam, assessment of concomitant medications, and collection of data on adverse events. Women of childbearing potential will undergo urine pregnancy tests at eligibility, enrollment and at each safety visit. Since MMF is FDA pregnancy category D, women involved in activity that could result in pregnancy will be required to use two forms of contraception. If women become pregnant during the study and are on a study medication, they will

Clinical Protocol

discontinue the medication immediately, and have no additional anoscopies if enrolled in the sub-study. Women will be asked, but will not be required, to allow the study staff to contact them after delivery to get information about their pregnancy outcome. Pregnant participants will be linked to care appropriate for pregnant women with HIV infection.

Participants will be closely monitored in a standardized fashion for potential toxicities and adverse events. Safety labs, including complete blood count, comprehensive metabolic panel, plasma HIV RNA concentrations and CD4 T cell counts will be monitored frequently as indicated in **Figure 1** and **Table 2**.

The Division of AIDS Table for Grading the Severity of Adult Adverse Events (DAIDS AE Grading Table), Version 1.0, dated December 2004, Clarification August 2009, will be used for screening eligibility and for grading toxicities and is available at <http://rsc.tech-res.com/safetyandpharmacovigilance>. Alternate explanations for clinical or laboratory abnormalities that may at first appear to be related to the study agent must be explored.

Management of adverse experiences will be according to the best clinical practice and the judgment of the site investigator. Participants with Grade 3 and 4 laboratory abnormalities will be asked to return to the clinic to have the test that is abnormal repeated, preferably within 72 hours. Laboratory norms will be the institutional values of the lab performing the tests. Abnormal clinical and laboratory findings will be followed until resolution to < Grade 2 or baseline.

- Grade 1 – Continue study drug; routine monitoring.
- Grade 2 – Continue study drug; monitor closely with more frequent visits when clinically indicated.

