(2) Potential risks from participation in this study include those related to blood draws. All personnel responsible for blood drawing will be experienced phlebotomists who will follow standard procedures. Blood draws can be uncomfortable and cause bruising. Some temporary anemia could occur from study phlebotomy. A record of all study phlebotomies and blood volume drawn will be maintained for each participant, and total blood collection for clinical care and the study will be monitored and IRB limits for study purposes will not be exceeded. Specifically, individual blood draws will never be more than 270 mL and total volumes of blood drawn over an eight-week period will never be more than 450 mL.

(3) Insertion of an anoscope may be uncomfortable. Rectal biopsies usually do not hurt. However, it is possible subjects could feel some brief pain or discomfort. In rare cases, these biopsies may

Clinical Protocol

cause a significant amount of bleeding or, rarely, an infection at the site that was sampled. In extremely rare circumstances, rectal biopsies can result in rectal perforation. Lidocaine cream may cause local numbness, redness, swelling or irritation. Extremely rare side effects include irregular heartbeat, shortness of breath and seizure. Precautions will be taken by the experienced study gastroenterologist at the time the biopsies are obtained to prevent perforation and to prevent or minimize bleeding and infection. In addition, as a further precaution, participants will be asked not to have anal sex for 5 days after the biopsies to help prevent any possible increase in risk of infection or bleeding.

(4) Answering questions about smoking, alcohol use, and sexual behaviors may make subjects feel uncomfortable.

(5) There are also potential risks related to confidentiality. All participating staff and faculty at the site will maintain the confidentiality of study subjects, and study materials that could expose identity will be kept in locked cabinets or in password-protected files, accessible only to the study personnel at the research clinic conducting the study with a need to know.

(6) Reports of MMF adverse reactions are based on dosages of 2-3 grams daily (rather than 1g daily in this study). A detailed description of all adverse effects and precautions is contained in the CellCept® Product Monograph, which is included in the Appendix to the Clinical Protocol. (Of note, we will be using the generic version of MMF and not CellCept.)

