The principal adverse reactions associated with the oral administration of MMF include diarrhea, leukopenia, sepsis, and nausea and vomiting. There also is evidence of a higher frequency of certain types of infections, e.g., cytomegalovirus viremia, JC virus-associated progressive multifocal leukoencephalopathy (PML) and polyomavirus-associated nephropathy (PVAN). Patients receiving MMF alone or as part of an immunosuppressive regimen are at increased risk of developing lymphomas and other malignancies, particularly of the skin. These risks appear to be related to the intensity and duration of immunosuppression rather than to the use of any specific agent.

There are also a small number of patients who received solid organ transplants and experienced reversible falls in their red cell or white cell counts while receiving MMF. Additionally, cases of Pure Red Cell Aplasia (PRCA) have been reported in some patients receiving MMF. PRCA is a condition in which the bone marrow stops producing red blood cells. In some instances, PRCA can be reversed by reducing or stopping MMF.

MMF has embryo-fetal toxicity, causing fetal harm when administered to a pregnant female. Use of MMF during pregnancy is associated with an increased risk of first trimester pregnancy loss and an increased risk of congenital malformations, especially external ear and other facial abnormalities including cleft lip and palate, and anomalies of the distal limbs, heart, esophagus, kidney and nervous system.

There will be adequate protection against risks including IRB approval at the study site, written informed consent, rapid reporting of adverse events and data safety monitoring as above.

(8) Use of ondansetron is occasionally associated with diarrhea, headache, fever, lightheadedness, dizziness, weakness, fatigue, constipation, rash, blurred vision, urinary retention, and muscle spasm.

(9) The most common adverse reactions ($\geq 20\%$) for Myfortic® include anemia, leukopenia, constipation, nausea, diarrhea, vomiting, dyspepsia, urinary tract infection, CMV infection,

Clinical Protocol

insomnia. Rare more severe complications include pure red cell aplasia and Progressive multifocal leukoencephalopathy (PML).

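### The hemoglobin exclusion limit in section 4.2(o) is printed in mg/dL, almost certainly for g/dL; taken literally it is 1000 times too low and excludes nobody

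*Combined protocol and SAP*

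**What the plan says.** Section 4.2, item o, sets laboratory exclusions under the lead-in "The following laboratory values (<30 days before enrollment". The first is "Hemoglobin < 8.5 mg/dL". The others concern neutrophils, ALT, platelets and creatinine clearance, and each is usable as printed.

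No other place in the document gives a hemoglobin or hematocrit limit for entry, or uses the unit g/dL. Two other places touch on anemia at screening:

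- Section 6.1 has routine bloods drawn at the eligibility visit, covering "blood cell counts and signs of anemia, kidney or liver dysfunction". It gives no threshold.
- Section 6.2 says that the DAIDS grading table "will be used for screening eligibility and for grading toxicities". Neither 4.1 nor 4.2 names a hemoglobin grade that excludes.

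Section 9.0 lists the related risks. On blood draws: "Some temporary anemia could occur from study phlebotomy". The most common Myfortic reactions "include anemia, leukopenia, constipation, nausea, diarrhea, vomiting, dyspepsia". On MMF, it describes reversible falls in red cell counts and adds that "cases of Pure Red Cell Aplasia (PRCA) have been reported in some patients receiving MMF".

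**The concern.** A value of 8.5 is a sensible hemoglobin limit only in g/dL. In mg/dL it lies far below any level a candidate could have, so the exclusion has no effect if applied as printed.

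This is a safety limit that the site applies to each candidate, in a trial that combines heavy early blood collection with drugs linked to anemia. Eligibility criteria are applied and audited as written. If the line were copied literally onto a screening form, the form would carry a check that always passes.

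**Working it through.** **Inputs**

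- Printed limit: 8.5 mg/dL (section 4.2, item o).
- Conversion: 1 g = 1000 mg.
- Assumed range of human hemoglobin, severe anemia included: 2 to 20 g/dL. This is an assumption; the documents give no range.
- Scheduled blood volumes in mL (Table 2, with sections 6.1 and 9.0).

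**Unit conversion**

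- Printed limit: 8.5 / 1000 = 0.0085 g/dL.
- Limit if g/dL was meant: 8.5 × 1000 = 8,500 mg/dL.
- Ratio of the two readings: 8,500 / 8.5 = 1000.

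**Distance of any candidate from the printed limit**

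- Low end: 2 g/dL = 2,000 mg/dL, and 2,000 / 8.5 ≈ 235.
- High end: 20 g/dL = 20,000 mg/dL, and 20,000 / 8.5 ≈ 2,353.

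**Who is excluded under each reading**

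| Hemoglobin (g/dL) | Excluded at 8.5 mg/dL | Excluded at 8.5 g/dL |
|---|---|---|
| 3 | no | yes |
| 5 | no | yes |
| 7 | no | yes |
| 8.4 | no | yes |
| 8.5 | no | no |
| 10 | no | no |
| 13 | no | no |

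**Could another part of the plan supply the limit?** The grading table cited in section 6.2 is external, and the protocol reproduces no hemoglobin value from it. A grading table becomes an entry limit only when the protocol says which grade excludes. Sections 4.1 and 4.2 do not say so for hemoglobin.

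**Context: blood volume early in the study.** Table 2 tracks "Rolling volumes/8 weeks (max 450mL").

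- Through the week 2 peak sample: 23 (eligibility) + 211 (entry) + 10.5 (week 1) + 31 + 15.5 (week 2 trough and peak) = 291.0 mL.
- Through the week 4 peak sample: 291.0 + 142 + 15.5 = 448.5 mL, which is 450 − 448.5 = 1.5 mL under the cap.

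The visit descriptions in section 6.1 agree with the table: 211 mL at entry, 10.5 mL at week 1, 46.5 mL at week 2 (31 + 15.5) and 157.5 mL at week 4 (142 + 15.5). For participants who are not escalated, week 4 comes after the lead-in, so their lead-in total is 291 mL. The cap is not breached. The sum shows only that hemoglobin at entry matters here; it is not evidence about the unit.

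**The case against.** The strongest reply is that nobody would be misled. The printed value is physiologically impossible, 8.5 has only one sensible unit, and this is a single-site study of five participants. The number itself is not disputed, only the unit prefix, and the ratio of 235 measures no effect on the trial.

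There are also safeguards:

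- Blood counts are scheduled at eligibility, entry and weeks 1 and 2 (Table 2).
- Under section 6.2, study drug is held for confirmed Grade 3 events and stopped for Grade 4 events, unless there is compelling evidence that the drug is not the cause.
- Under section 6.4, the investigator may withdraw anyone whose health would suffer from staying in.
- Section 9.0 requires a phlebotomy record for each participant and adherence to the IRB volume limits.

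Most of this stands, and it is why the point ranks low. It does not make the criterion correct. The hold, stop and withdrawal rules act after enrollment, whereas this limit is meant to act before it. A blood count at eligibility excludes nobody unless it is compared with a usable threshold. If the intended unit is obvious, correcting it should be uncontroversial.

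**Conclusion.** The point holds. As printed, the limit equals 0.0085 g/dL and excludes nobody, given the assumed range of 2 to 20 g/dL; any realistic range leads to the same conclusion. That g/dL was meant is an inference from the size of the number, so the sponsor should confirm it. On that reading the printed limit is wrong by a factor of 1000.

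The error sits in an operative safety criterion, not in background text, and nothing else in the documents supplies a hemoglobin limit. The practical consequence is small: no wrongful enrollment is shown or claimed, and the endpoint, sample size and analysis do not depend on it. The correction is desirable rather than essential.

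**What to change.** In section 4.2, item o, change the hemoglobin unit from mg/dL to g/dL once the sponsor has confirmed it, keeping the value 8.5. Check that the screening form carries the same unit. No new threshold is proposed.

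The change is one unit in the next amendment or in a clarification note, with no cost to conduct or analysis.

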4.3 Disallowed Medications

- a. Proton pump inhibitors

Clinical Protocol

- b. Rifampin
- c. Cholestyramine
- d. Colestipol
- e. Estrogen or progestin contraceptive
- f. Cyclosporine, tacrolimus or pimecrolimus
- g. Fingolimod
- h. Leflunomide
- i. Magnesium salts
- j. Metronidazole (oral)
- k. Monoclonal antibodies
- l. Tofacitinib
- m. Systemic corticosteroids

4.4 Eligibility and Enrollment

Protocol enrollment is available to all interested qualified individuals willing to adhere to the study. Written informed consent for study participation must be obtained before any study-related procedures are performed. Participant enrollment evaluation follows the Schedule of Evaluations (Table 2 and Section 12.0).

4.5 Sub-Study Procedures

Co-enrollment into observational studies is allowed if blood volumes permit. Co-enrollment into other interventional studies will be considered by the study team on a case-by-case basis, and will depend upon blood volumes, whether participation is likely to interfere with completion of this study or the outcome of this study.

